## **8.2 Determination of Sample Size**

Based on actual real-world pragmatic enrollment observed in the ongoing study, more non-cirrhotics and less compensated cirrhotic subjects are enrolling than was previously projected. This will improve precision for the point estimated SVR12 rates of the non-cirrhotic patient and decrease precision for the point estimated SVR12 rates in compensated cirrhotic subjects. For the comparison between Arm A and Arm B in non-cirrhotic subjects, if the observed SVR12 rate in Arm B is 92%-96%, with 100 subjects in Arm A and 50 subjects in Arm B, the half widths of 95% confidence interval of the difference between SVR12 rates are displayed in the table below:

SVR12 in Arm B	92%	93%	94%	95%	96%
Half width (SVR12 in Arm A = SVR12 in Arm B)	0.092	0.087	0.081	0.074	0.067
Half width (SVR12 in Arm A = SVR12 in Arm B – 1%)	0.094	0.088	0.083	0.076	0.069
Half width (SVR12 in Arm A = SVR12 in Arm B – 2%)	0.095	0.090	0.085	0.078	0.072

For the comparison between Arm C and Arm D in cirrhotic subjects, if the observed SVR12 rate in Arm D is 94%-98%, with 40 subjects in Arm C and 40 subjects in Arm D, the half widths of the 95% confidence interval of the difference between SVR12 rates are displayed in the table below:

SVR12 in Arm D	94%	95%	96%	97%	98%
Half width (SVR12 in Arm C = SVR12 in Arm D)	0.104	0.096	0.086	0.075	0.061
Half width (SVR12 in Arm C = SVR12 in Arm D - 1%)	0.108	0.100	0.091	0.081	0.068
Half width (SVR12 in Arm C = SVR12 in Arm D - 2%)	0.112	0.104	0.095	0.086	0.075

In Study M15-410, subjects with prior NS5A inhibitor experience only (ie. PI naïve) had an SVR12 rate of 94.4% for 16 weeks treatment duration. This SVR12 rate would give half widths of 95% confidence intervals of  $\leq 11\%$  in most cases where Arm A or Arm C are no more than 1% worse than Arm B or Arm D, respectively.

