### **3.4                   Study Rationale**

The FDA approved label duration for NS5A-experienced, PI-naïve subjects with or without compensated cirrhosis and HCV GT1 chronic infection is G/P 300 mg/120 mg for 16 weeks. However, the G/P regimen may be further refined based on additional efficacy results in subsets of

NS5A inhibitor experienced, PI-naïve HCV GT1 infected subjects. The goals of this study are to increase the confidence in real world DAA failure patients who are receiving the recommended G/P regimen, to explore a shorter 12-week duration of the G/P regimen in non-cirrhotic subjects, and ribavirin-intensification of a shorter 12-week duration of the G/P regimen in subjects with compensated cirrhosis.

High SVR12 rates were achieved with G/P 300 mg/120 mg when given for 12 and 16 weeks in GT1-infected subjects who were NS5A-experienced and PI-naïve (SVR12 90.0% 18/20 and 94% 17/18, respectively, MAGELLAN-1, NCT02446717, AbbVie, data on file). The majority of subjects with prior NS5A inhibitor-experience in MAGELLAN-1 Part 1 & 2 combined were subjects who failed prior LDV/SOF (Harvoni) treatment: GLE/PIB 300 mg/ 120 mg for 12 weeks (n=12, 11 achieved SVR12, 91.7%), GLE/PIB 300 mg/ 120 mg for 16 weeks (n=10, 9 achieved SVR12, 90.0%), and G/P 300 mg/ 120 mg plus 800 mg once daily RBV for 12 weeks (n=4, all 4 achieved SVR12). Among the 42 NS5A-experienced and PI-naïve failures enrolled in MAGELLAN-1, 30/31 (96.8%) subjects without cirrhosis and 9/11 (81.8%) of subjects with compensated cirrhosis achieved an SVR12.

In MAGELLAN-1, NS5A inhibitor-experienced, PI-naïve subjects without cirrhosis who received G/P 300 mg/120 mg for 12 and 16 weeks achieved SVR12 rates of 92.3% (12/13) and 100% (14/14), respectively. As the difference in SVR12 between these two durations was based on a single subject that did not achieve SVR, it is hypothesized that 12 weeks treatment duration with G/P may provide an effective retreatment option. Therefore, the present study will evaluate G/P for 12 and 16 weeks in a larger patient population to determine if treatment duration may be decreased from 16 to 12 weeks in NS5A inhibitor-experienced, PI-naïve subjects without cirrhosis.

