MAGELLAN-1 enrolled a total of 11 NS5A inhibitor -experienced, PI-naïve subjects with compensated cirrhosis; 85.7% (6/7) and 75.5% (3/4) subjects achieved SVR12 with G/P 300 mg/120 mg for 12 or 16 weeks, respectively. The two subjects that did not achieve SVR12 experienced on-treatment virologic failure and may benefit from the addition of RBV which has

been shown to decrease the risk of both on-treatment failure and relapse. Therefore, the present study will evaluate G/P for 16 weeks and G/P + RBV for 12 weeks in NS5A inhibitor -experienced, PI-naïve subjects with compensated cirrhosis.

The objective of this study is therefore to obtain additional data with G/P in NS5A inhibitor-experienced, PI-naïve GT1-infected subjects that will help to optimize the G/P regimen for this population. The initial study design did not exclude patients with historical PI exposure prior to the NS5A-inbitor exposure as PI resistance has been shown to quickly revert to wild types, but did exclude only those who received a PI in combination with a NS5a. Since the initial study launch, G/P has been approved by the FDA and was given a label for NS5A experienced, PI naïve patients only; with 16 weeks of therapy. Thus, to minimize treatment failure in this population and more accurately reflect FDA label duration, patients with any prior PI exposure will be excluded from further recruitment into the study and any patient already enrolled or randomized to a 12-week arm will have their treatment extended to 16 weeks duration.

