## **8.0 Statistical Methods and Determination of Sample Size**

### **8.1 Statistical and Analytical Plans**

The primary analysis will occur after all subjects in the Main Study have completed the PT Week 12 Visit or prematurely discontinued study. The data for subjects treated in the Main study will be locked after data cleaning. Data from the Retreatment sub-study will be analyzed separately as described below and be included in the end-of study analysis.

The data analysis will be generated using SAS/STAT software, version 9.4 or higher of the SAS system for Windows. Copyright © [2001-2012] SAS Institute Inc. SAS and all other SAS Institute Inc. product or service names are registered trademarks or trademarks of SAS Institute Inc., Cary, NC, USA. All statistical tests (if applicable) and confidence intervals will be two-sided with an alpha level of 0.05. Descriptive statistics will be provided, such as the number of observations (N), mean, and standard deviation (SD) for continuous variables and counts and percentages for discrete variables.

The primary efficacy analyses in the Main study will be performed on the intention to treat population summarized according to the treatment arm in which the subject actually received treatment. This primary efficacy analysis dataset will be referred to as the modified ITT (mITT) population and defined as all enrolled subjects who receive at least one dose of study drug according to each subject's final treatment arm assignment (Arm A, Arm B, Arm C or Arm D). Analyses in the Retreatment sub-study will be performed overall on the Evaluable Patient population for that sub-study (EP-RS) defined as all subjects who receive at least one dose of study drug in the Retreatment sub-study.

The traditional ITT population, which includes all subjects who received at least one dose of study drug categorized by the patients' randomized treatment arm, along with other modified ITT populations will be employed in the sensitivity analyses. Specifically, sensitivity analyses of the primary endpoint of the Main Study will be performed on the following modified ITT populations:

- 1) Modified ITT-Genotype (mITT-GT) Population
  - includes the mITT population (or “as treated”) but excludes subjects with genotype other than GT1 infection.
- 2) Modified ITT- Genotype and Virologic Failure (mITT- GT-VF) Population

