### **8.1.2.1 Primary Efficacy Endpoints**

The primary efficacy endpoints for the mITT population are the difference in SVR12 (HCV RNA < LLOQ 12 weeks after the last actual dose of study drug) rates between Arm A and Arm B in non-cirrhotic subjects, and difference in SVR12 rates between Arm C and Arm D in cirrhotic subjects.

The difference in SVR12 rates will be summarized with a two-sided 95% confidence interval for the comparison between Arm A and Arm B in non-cirrhotic subjects, and for the comparison between Arm C and Arm D in cirrhotic subjects. The number and percentage of subject achieving SVR12 by treatment arm will also be summarized with a two-sided 95% confidence interval. The confidence interval for the difference in SVR12

rates will be calculated using Wilson's score method. The confidence interval for the SVR12 rates by treatment arm will be calculated using the normal approximation to the binomial distribution if the number of subjects who failed to achieve SVR12 is at least 5. If the number of subjects who failed to achieve SVR12 is less than 5, Wilson's score method will be used instead.

A summary of reasons for SVR12 non-response (e.g., on-treatment virologic failure, relapse, other) will be provided.

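### Section 8.2 gives Arm C vs D precision only for SVR12 rates of 94-98% and supports it with a mostly non-cirrhotic 94.4%; the protocol's own cirrhotic results imply wider intervals

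*Protocol*

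**What the plan says.** Section 8.2 has two tables of 95% confidence-interval half-widths for the difference in SVR12. For Arms A and B the condition is "if the observed SVR12 rate in Arm B is 92%-96%, with 100 subjects in Arm A and 50 subjects in Arm B". For Arms C and D it is "if the observed SVR12 rate in Arm D is 94%-98%, with 40 subjects in Arm C and 40 subjects in Arm D". In each table the 12-week arm is set equal to, one point below or two points below the 16-week arm. The cirrhotic half-widths run from 0.061 to 0.112.

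The section then notes that NS5A-experienced, PI-naïve subjects in Study M15-410 "had an SVR12 rate of 94.4% for 16 weeks treatment duration". From this it concludes that half-widths are at most 11% in most cases where Arm A or Arm C is no more than one point worse than its comparator. One rate therefore serves both strata.

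Section 3.4 splits the same prior data by cirrhosis. Overall, 30/31 subjects without cirrhosis reached SVR12, but only "9/11 (81.8%) of subjects with compensated cirrhosis achieved an SVR12". By duration (12, then 16 weeks), non-cirrhotic subjects had 12/13 and 14/14, and in cirrhotic subjects "85.7% (6/7) and 75.5% (3/4) subjects achieved SVR12".

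On method, section 8.1 says that "confidence intervals will be two-sided with an alpha level of 0.05", and section 8.1.2.1 says that the interval for the difference in SVR12 "rates will be calculated using Wilson's score method".

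**The concern.** The planning ranges run against the protocol's own evidence. Cirrhotic Arm D is given a higher SVR12 range than non-cirrhotic Arm B, with no reason stated, while section 3.4 reports a lower rate in cirrhotics and uses their failures to motivate adding ribavirin in Arm C. The rate that carries the 11% statement comes mainly from the other stratum: 14 of its 18 subjects had no cirrhosis.

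Arm C vs D is one of the two primary efficacy comparisons. Near 100% the binomial variance rises quickly as the rate falls, so the choice of range largely sets the precision shown. Someone reading section 8.2 alone would expect the cirrhotic difference to be estimated to within about 6 to 11 points. At the cirrhotic rates the protocol itself cites, it would be about 15 to 19.

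**Working it through.** **Inputs.** Two-sided 95% intervals (8.1); 40 per cirrhotic arm and Arm D at 94-98% (8.2); 94.4% at 16 weeks (8.2); prior counts (3.4).

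**Step 1: what 94.4% is.** Section 3.4 gives 17/18 at 16 weeks, and 17/18 = 94.4%. The split is 14/14 without and 3/4 with cirrhosis: (14 + 3)/(14 + 4) = 17/18. The cirrhotic part alone is 3/4 = 75.0% (the text prints 75.5%). Adding the 12-week 6/7 gives (6 + 3)/(7 + 4) = 9/11 = 81.8%. All 11 cirrhotic subjects are thus accounted for by G/P without ribavirin.

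**Step 2: reproduce the table.** The unpooled normal (Wald) half-width is

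h = 1.96 × √[pC(1 − pC)/nC + pD(1 − pD)/nD].

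- pC = pD = 0.94, 40 per arm: 0.94 × 0.06 = 0.0564; 2 × 0.0564/40 = 0.00282; square root 0.0531; × 1.96 = 0.104. Stated: 0.104.
- pC = pD = 0.98: 2 × 0.0196/40 = 0.00098; square root 0.0313; × 1.96 = 0.061. Stated: 0.061.

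The formula reproduces all 15 cirrhotic and all 15 non-cirrhotic cells to three decimals. The table is correct for its inputs.

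**Step 3: the case behind the 11% statement.** With pD = 0.944 and pC = 0.934: 0.0529 + 0.0616 = 0.1145; /40 = 0.00286; square root 0.0535; × 1.96 = 0.105. This is within 11%.

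**Step 4: other rates, 40 per arm.** The Wilson column takes the planned method for a difference to be Newcombe's interval, built from the two arms' Wilson limits. The ratio is the normal half-width divided by 0.105.

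| Arm D rate | Arm C | Normal formula | Wilson-based | Ratio |
|---|---|---|---|---|
| 95% | equal | 0.096 | 0.121 | 0.91 |
| 94.4% | 1 point lower | 0.105 | 0.126 | 1.00 |
| 92% | equal | 0.119 | 0.135 | 1.13 |
| 90% | equal | 0.131 | 0.144 | 1.25 |
| 85.7% (6/7) | equal | 0.153 | 0.159 | 1.46 |
| 81.8% (9/11) | equal | 0.169 | 0.171 | 1.61 |
| 75% (3/4) | equal | 0.190 | 0.186 | 1.81 |

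For C-D the 11% statement already fails at 92%, the lower end of the range used for non-cirrhotics. By the Wilson-based method it fails at 94.4% too (0.126). For A-B it holds throughout the tabulated range: the largest half-width is 0.095 by the normal formula and 0.103 by the Wilson-based method.

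**Step 5: how firm the prior rates are.** 95% Wilson limits are 52.3-94.9% for 9/11, 30.1-95.4% for 3/4 and 48.7-97.4% for 6/7. Exact upper limits are 97.7% for 9/11 and 99.4% for 3/4.

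**Side check.** The enrolment cap of 75 cirrhotics gives 37 and 38 per arm, not 40. The normal half-widths are then 0.175 at 81.8% and 0.196 at 75%.

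**The case against.** The best defence is that the table is an explicit conditional display, correct for its stated rates, with no power claim, margin or test attached. The primary analysis will report the observed interval, so the actual precision will be visible. Section 8.2 already warns of lower precision in cirrhotics, though it attributes this to enrolment, and it limits the 11% statement to most cases. All of this stands and limits the consequence. It does not cover the closing sentence, which uses a pooled rate to support a precision figure for Arm C.

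The prior cirrhotic data are also tiny, and 3/4 is part of 9/11, so they are not separate sources. They cannot establish that 94% is wrong. Arm C adds ribavirin, which section 3.4 expects may help with the failures seen, so using the earlier rates for Arm C is an assumption. The tabulated range, however, is for Arm D, which has no ribavirin, and every row puts Arm C at or below Arm D.

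Table 2 of the protocol reports 98/101 (97.0%) in GT1 cirrhotics, inside the 94-98% range. Those were treatment-naïve or TE-PRS subjects, a different population, and section 8.2 does not cite the figure.

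A reader might go further and infer that the rates of 96-98% are ruled out by the protocol's data. That depends on the interval chosen: the Wilson upper limit for 6/7 is 97.4%, and the exact limits for 9/11 and 3/4 reach 97.7% and 99.4%.

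**Conclusion.** The point holds as a fault in the choice of planning rates, not in arithmetic. Section 8.2 shows cirrhotic precision only for rates above every cirrhotic rate the protocol reports in the target population, and it supports this with a figure that is not a cirrhotic rate.

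If the cited cirrhotic rates hold, the C-D half-width at 40 per arm is about 0.17 (81.8%) to 0.19 (75%), about 1.6 to 1.8 times the 0.105 behind the 11% statement. At 92% to 90% it is 0.12 to 0.13, about 1.1 to 1.25 times. These figures assume equal rates in the two arms and the section's own formula.

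A reader might infer an unconditional overstatement of up to threefold. The documents do not support that: the top of such a range sets 75% against the 98% cell (0.190/0.061 = 3.1), whereas section 8.2 draws its conclusion at 94.4%, and the low rates rest on 11 and 4 subjects. A true rate of 94% remains possible, so the remedy is a wider range of scenarios, not a single replacement value.

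**What to change.** In section 8.2:

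- extend the Arm D range downward to cover the protocol's own cirrhotic results, for example 75% to 95%;
- state that 94.4% pools 14/14 non-cirrhotic and 3/4 cirrhotic subjects;
- limit the statement of at most 11% to Arm A vs B;
- give the C-D half-width over 75-95% as about 10 to 19 points by the present normal-approximation formula (0.096 to 0.190), or about 12 to 19 points by the planned Wilson score method (0.121 to 0.186), and name the method used.

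This changes protocol wording only and needs no extra patients. The cost is that the stated precision of the cirrhotic comparison becomes less favourable.

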**Number of Subjects to be Enrolled:** up to 225 subjects**\*Applicable to Retreatment sub-study only**

**Methodology:**

**Main Study:**

This is a Phase 3b, randomized, open-label, pragmatic, multicenter study to evaluate efficacy and safety of the fixed-dose combination tablets of glecaprevir/pibrentasvir with or without RBV in NS5A-inhibitor plus sofosbuvir ± RBV-experienced, chronic HCV GT1-infected subjects. Up to 225 subjects at approximately 35 sites will be enrolled into four study arms A, B, C and D. Up to 150 non-cirrhotic subjects will be randomized in a 2:1 ratio to Arms A and B, and up to 75 subjects with compensated cirrhosis will be randomized in a 1:1 ratio to Arms C and D. Randomization will be stratified by HCV genotype 1 subtype (1b or non-1b).

Subjects without cirrhosis will be randomized 2:1 to:

Arm A: G/P 300 mg/120 mg QD for 12 weeks

Arm B: G/P 300 mg/120 mg QD for 16 weeks

Subjects with compensated cirrhosis will be randomized 1:1 to:

Arm C: G/P 300 mg/120 mg QD + weight-based RBV BID (1000 mg or 1200 mg total daily dose) for 12 weeks

Arm D: G/P 300 mg/120 mg QD for 16 weeks

Subjects who complete or prematurely discontinue the treatment will be followed for 12 weeks to monitor HCV RNA and to evaluate efficacy and the emergence and persistence of viral variants.

Scheduled visits for subjects in the planned Treatment Period consist of Day 1, Weeks 4, 8, 12 for all subjects and Week 16 for subjects in Arms B and D. During the Post-Treatment Period, subjects will have visits at Weeks 4 and 12 following completion of the Treatment Period. Efficacy and safety data will be monitored throughout the study. These data will enable assessment of virologic stopping, futility, and treatment extension criteria as described in the protocol.

---

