**Efficacy:**

The primary efficacy endpoints for the mITT population are the difference in SVR12 (HCV RNA < LLOQ 12 weeks after the last actual dose of study drug) rates between Arm A and Arm B in non-cirrhotic subjects, and difference in SVR12 rates between Arm C and Arm D in cirrhotic subjects.

The difference in SVR12 rates will be summarized with a two-sided 95% confidence interval for the comparison between Arm A and Arm B in non-cirrhotic subjects, and for the comparison between Arm C and Arm D in cirrhotic subjects. The number and percentage of subjects achieving SVR12 by treatment arm according to final treatment arm assignment of subjects will also be summarized with a two-sided 95% confidence interval. The confidence interval for the difference in SVR12 rates will be calculated using Wilson's score method. The confidence interval for the SVR12 rates by treatment arm will be calculated using the normal approximation to the binomial distribution if the number of subjects who failed to achieve SVR12 is at least 5. If the number of subjects who failed to achieve SVR12 is less than 5, Wilson's score method will be used instead.

The secondary efficacy variables are:

1. The difference in SVR12 rates between G/P given for 12 weeks (Arm A and C combined) and G/P given for 16 weeks (Arm B and D combined);
2. The percentage of subjects with on-treatment virologic failure;
3. The percentage of subjects with post-treatment relapse.

For the Main study, the differences in the percentages of subjects with on-treatment virologic failure or post-treatment relapse for non-cirrhotic subjects (Arm A vs Arm B) and subjects with compensated cirrhosis (Arm C vs Arm D) will be summarized along with 95% Wilson score intervals. Additional efficacy endpoints and efficacy subgroup analyses will be performed.

As an additional efficacy endpoint, the percentage of retreated subjects achieving SVR12 will be analysed on the EP-RS population overall for the Retreatment sub-study.

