##### **Randomization scheme:**

-GT1 non-cirrhotic (up to 150) subjects: randomized 2:1 to Arms A or B.

-GT1 cirrhotic (up to 75) subjects: randomized 1:1 to Arm C or D.

[figure not shown]
Randomization will be stratified by HCV GT 1b vs non-1b.

The Main study consists of 2 periods:

**Treatment Period:** Eligible subjects will be enrolled to receive G/P 300 mg/120 mg QD +/- RBV for 12 weeks or G/P for 16 weeks.

**Post Treatment Period:** Subjects who complete or prematurely discontinue the Treatment Period will be followed for 12 weeks after their last dose of study drug to evaluate efficacy and to monitor HCV RNA and the emergence and persistence of viral substitutions.

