**Figure 1.** **Study Schematic**

The study is designed to enroll up to 225 subjects with a minimum number of 175 subjects to meet scientific objectives and without enrolling an undue number of subjects in alignment with ethical considerations. Therefore, if the target number of subjects has been enrolled, there is a possibility that additional subjects in screening will not be enrolled.

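### Section 8.2 states precision from Wald intervals and 80 cirrhotic subjects, but the protocol plans a Wilson score interval and caps cirrhotics at 75, so the 11% half-width claim fails for Arm C vs Arm D

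*Protocol*

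**What the plan says.** Section 8.2 gives no power calculation and no margin. It tabulates half-widths of the 95% interval for the SVR12 difference:

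- A vs B with 100 and 50 subjects, Arm B at 92% to 96%: 0.067 to 0.095.
- C vs D "with 40 subjects in Arm C and 40 subjects in Arm D", Arm D at 94% to 98%: 0.061 to 0.112.

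It then takes 94.4% from Study M15-410 (16 weeks, NS5A-experienced, PI-naïve) and says the half-widths are at most 11% "in most cases where Arm A or Arm C are no more than 1% worse than Arm B or Arm D".

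Other sections differ on two inputs. On numbers, the Synopsis says "up to 75 subjects with compensated cirrhosis will be randomized in a 1:1 ratio to Arms C and D", and Section 5.1 repeats it: "GT1 cirrhotic (up to 75) subjects: randomized 1:1 to Arm C or D". On method, the Synopsis says "The confidence interval for the difference in SVR 12 rates will be calculated using Wilson's score method", and Section 8.1.2.1 says the same. Section 8.1 sets the level: "confidence intervals will be two-sided with an alpha level of 0.05". Section 8.2 names no method for its tables.

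**The concern.** The half-widths are the whole quantitative case for the sample size, and C vs D is one of the two primary efficacy comparisons. If the tables come from a different interval than the one to be reported, and from more cirrhotic subjects than may be enrolled, readers will expect a tighter answer in cirrhotics than the trial can give.

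The Wald interval is at its most optimistic where these tables sit. At response rates of 92% to 98% with 40 to 100 subjects per arm, its width shrinks towards zero as the rate nears 100%, and a score interval's does not.

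**Working it through.** **Inputs.** z = 1.96 (Section 8.1). Arm sizes 100/50 and 40/40, the rate grids and the 94.4% anchor (Section 8.2). Cap of 75 cirrhotics at 1:1, hence 37/38 (Synopsis, Section 5.1). Wilson's score method for the difference (Synopsis, Section 8.1.2.1).

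**Step 1: reproduce the printed tables.** Unpooled Wald half-width: 1.96 × √[p₁(1−p₁)/n₁ + p₂(1−p₂)/n₂].

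- A and B both 92%, 100/50: 1.96 × √[0.92 × 0.08 × (1/100 + 1/50)] = 0.092 (printed 0.092).
- C and D both 94%, 40/40: 1.96 × √[2 × 0.94 × 0.06/40] = 0.104 (printed 0.104).
- C and D both 98%, 40/40: 0.061 (printed 0.061).

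All 30 cells match to rounding (largest deviation 0.0005).

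**Step 2: check the numbers.** 40 + 40 = 80, above 75. 100 + 50 + 40 + 40 = 230, above the overall limit of 225. Keeping Wald and using 37/38, the C vs D range becomes 0.063 to 0.116, an increase of 0.002 to 0.004 per cell. At 94.4% it is 0.104 (equal) or 0.108 (C 1 point lower), so the cap alone does not break the 11% statement.

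**Step 3: use the planned method.** Wilson limits for one arm: [p + z²/2n ± z√(p(1−p)/n + z²/4n²)] / (1 + z²/n). The Newcombe interval for p_C − p_D combines them:

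- lower = (p_C − p_D) − √[(p_C − l_C)² + (u_D − p_D)²]
- upper = (p_C − p_D) + √[(u_C − p_C)² + (p_D − l_D)²]

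The interval is asymmetric, so half of the total width is used.

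Example with D = 94.4% (n = 38) and C = 93.4% (n = 37). Wilson limits are 0.8068 to 0.9796 for C and 0.8225 to 0.9840 for D.

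- lower = −0.010 − √(0.1272² + 0.0400²) = −0.143
- upper = −0.010 + √(0.0456² + 0.1215²) = 0.120
- half-width = (0.143 + 0.120)/2 ≈ 0.132

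| Comparison | Printed | Newcombe, same n | Newcombe, within cap |
|---|---|---|---|
| C vs D, full grid | 0.061–0.112 (40/40) | 0.103–0.131 | 0.108–0.136 (37/38) |
| C vs D at 94.4%, equal / C 1 point lower | – | 0.124 / 0.126 | 0.129 / 0.132 |
| A vs B, full grid | 0.067–0.095 (100/50) | 0.081–0.103 | unchanged |
| A vs B at 94.4%, equal / A 1 point lower | – | 0.090 / 0.091 | unchanged |

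**Step 4: test the 11% statement.** Of the 10 C vs D cells with C equal or 1 point lower, all 10 are at most 0.11 as printed, 3 are under Newcombe at 40/40, and 1 is at 37/38. For A vs B all 10 stay within 0.11 (largest 0.102).

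**Step 5: a floor.** With no failures in either arm the Newcombe half-width is still 0.088 at 40/40 and 0.093 at 37/38. Printed cells such as 0.061, 0.068 and 0.075 therefore cannot arise from this interval.

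**Step 6: sensitivity to the cirrhotic rate.** Section 3.4 gives 17/18 (94.4%) for 16 weeks, which is 14/14 non-cirrhotic plus 3/4 cirrhotic. Cirrhotics over both durations were 6/7 + 3/4 = 9/11 (81.8%). With equal rates at 37/38, the Newcombe half-width is about 0.15 at 90%, 0.18 at 81.8% and 0.19 at 75%.

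**The case against.** The strongest reply is that nothing decisional rests on Section 8.2. There is no test, margin or power, and the primary intervals will be reported at their true width whatever the planning table says. The section also concedes that fewer cirrhotics will reduce precision. This stands, and it limits the consequence. It does not make the stated figures right.

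Second, the printed cells are correct for the formula used, and a Wald approximation is common in planning. That also stands: the fault is a mismatch of inputs and method, not a slip in calculation. But the protocol allows the normal approximation only for single-arm rates with at least five failures; for the difference it names Wilson's method without condition.

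Third, the protocol does not say which Wilson-type interval for a difference it means. Newcombe is an assumption. The Miettinen-Nurminen score interval gives 0.132 and 0.135 for C vs D at 94.4% with 38/37, so the choice affects the third decimal and not the conclusion.

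Two stronger readings are tempting. A reader might infer from 9/11 and 3/4 (printed as "85.7% (6/7) and 75.5% (3/4) subjects achieved SVR12", though 3/4 is 75.0%) that the 94% to 98% grid is wrong and the true half-width is about 0.18. The documents do not support that. The grid is conditional on the observed rate. The Wilson 95% interval for 9/11 runs from about 52% to 95%, so 94% is not excluded. And all 11 subjects received G/P without ribavirin, so they say nothing direct about Arm C. A reader might also fault the design "with a minimum number of 175 subjects to meet scientific objectives" for showing no precision at that size. Section 5.1 attaches no precision claim to the minimum and fixes no split between cirrhotic and non-cirrhotic subjects there, so this is an omission at most.

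**Conclusion.** The point holds for two inputs to Section 8.2: the interval method in both tables and the number of cirrhotics in the second. Under the planned method and the cap, each C vs D cell is wider than printed by about 0.02 to 0.05, and at 94.4% the half-width is about 13 points rather than at most 11. The A vs B figures are also too narrow, by about 0.01, but the 11% statement survives there. The interval accounts for most of the gap.

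This rests on reading Wilson's score method as Newcombe's combination of Wilson limits, on half of the total width as the measure, and on full recruitment of 75 cirrhotics. Fewer would widen C vs D further. The effect is overstated precision for one primary comparison, not an invalid analysis. Lower cirrhotic rates belong in the table as a sensitivity range and not as a correction.

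**What to change.** In Section 8.2:

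1. Recompute both tables with the planned score interval, naming the variant, and with no more than 37/38 subjects for C vs D.
2. Replace the single 11% sentence with one statement per comparison at 94.4%, the 12-week arm equal or 1 point lower: about 9% for A vs B and about 13% for C vs D.
3. As a recommended addition, extend the C vs D table to lower rates (about 0.15 at 90%, 0.18 at 81.8%, 0.19 at 75%). Note that the 94.4% anchor pools cirrhotic and non-cirrhotic subjects, and that 11 cirrhotic subjects without ribavirin do not exclude 94%.

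The cost is a rewrite of one section and a less favourable stated precision. Enrolment, treatment, endpoints and the planned analysis stay as they are.

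### The half-width tables in Protocol 8.2 are Wald, but the primary interval is fixed as Wilson's score method; under it the C-D half-widths are 17-67% larger and the 11% statement fails for C-D, though it holds for A-B

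*Protocol*

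**What the plan says.** Protocol 8.1.2.1 sets the method for the primary comparisons: the interval for the difference in SVR12 "rates will be calculated using Wilson's score method". The synopsis fixes the same method. Section 8.1 adds that "confidence intervals will be two-sided with an alpha level of 0.05".

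Protocol 8.2 gives two tables of half-widths for those same differences. The A-B table is set up "with 100 subjects in Arm A and 50 subjects in Arm B", with Arm B at 92% to 96%. The C-D table is set up "with 40 subjects in Arm C and 40 subjects in Arm D", with Arm D at 94% to 98%. Each has rows for a 12-week arm that is equal, 1 point worse or 2 points worse. Of the second table the section says that "the half widths of the 95% confidence interval of the difference between SVR12 rates are displayed in the table below". Neither table says how the interval was computed.

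The section closes with the 94.4% seen for 16 weeks in Study M15-410. "This SVR12 rate would give half widths of 95% confidence intervals of" at most 11%, it says, in most cases where Arm A or Arm C is no more than 1 point worse than its comparator. The sentence covers both comparisons together.

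**The concern.** With SVR12 close to 1 and about 40 subjects per arm, a Wald interval is much narrower than one built from Wilson limits. If the planning tables use the first and the analysis uses the second, the promised precision belongs to a different interval from the one that will be reported.

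Section 8.2 states no power, hypothesis or margin, so these half-widths are the only quantitative support for the sample size. The section itself concedes that the enrolment shift reduces precision in cirrhotic subjects. If the tables then understate how wide the C-D interval will be, readers are misinformed on the smaller of the two primary comparisons.

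**Working it through.** **Inputs.** z = 1.960 (two-sided 0.05, Protocol 8.1). Arm sizes 100/50 and 40/40, the rate grids and the reference rate 94.4% are from Protocol 8.2. The cap of 75 cirrhotic subjects, about 37/38 per arm, is from the synopsis and 5.1. Throughout, p1 is the 12-week arm and p2 the 16-week arm.

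**Step 1: reproduce the stated tables.** Unpooled Wald half-width = z × sqrt[p1(1−p1)/n1 + p2(1−p2)/n2].

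- C-D, 94%/94%: 1.960 × sqrt(2 × 0.94 × 0.06/40) = 0.1041; stated 0.104.
- C-D, 98%/98%: 1.960 × sqrt(2 × 0.98 × 0.02/40) = 0.0614; stated 0.061.
- A-B, 92%/92%: 1.960 × sqrt(0.92 × 0.08 × (1/100 + 1/50)) = 0.0921; stated 0.092.

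All 30 cells agree to rounding. The Newcombe-Wilson interval, with or without continuity correction, reproduces none of them.

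**Step 2: the planned method.** With Wilson limits (l, u) for each arm:

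- lower distance = sqrt[(p1−l1)² + (u2−p2)²]
- upper distance = sqrt[(u1−p1)² + (p2−l2)²]
- half-width = mean of the two distances.

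C-D at 40/40, stated → planned:

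| Arm D | Equal | 1 point worse | 2 points worse |
|---|---|---|---|
| 94% | 0.104 → 0.126 | 0.108 → 0.128 | 0.112 → 0.131 |
| 95% | 0.096 → 0.121 | 0.100 → 0.123 | 0.104 → 0.126 |
| 96% | 0.086 → 0.115 | 0.091 → 0.118 | 0.095 → 0.120 |
| 97% | 0.075 → 0.109 | 0.081 → 0.112 | 0.086 → 0.115 |
| 98% | 0.061 → 0.103 | 0.068 → 0.106 | 0.075 → 0.109 |

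Using unrounded values, planned/Wald runs from 0.1307/0.1117 = 1.17 to 0.1025/0.0614 = 1.67. Taken the other way, the stated values fall short by about 14% to 40% of the planned ones.

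For A-B at 100/50 the planned half-widths are 0.081-0.103 against the stated 0.067-0.095, which is 8% to 22% larger.

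**Step 3: the 11% statement at 94.4%.** The Wilson limits for 94.4% are 0.8267 and 0.9835 (n = 40), 0.8804 and 0.9747 (n = 100), and 0.8432 and 0.9814 (n = 50).

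- C-D, equal: both distances are sqrt(0.1173² + 0.0395²) = 0.124; Wald 0.101.
- C-D, 1 point worse: 0.126; Wald 0.105.
- A-B, equal: lower sqrt(0.0636² + 0.0374²) = 0.074, upper sqrt(0.0307² + 0.1008²) = 0.105, mean 0.090; Wald 0.078.
- A-B, 1 point worse: 0.091; Wald 0.080.

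Both A-B cases meet 11% and both C-D cases miss it. In the C-D rows for equal and 1 point worse, all 10 stated cells are within 11%; under the planned method 3 of 10 are (97% equal, 98% equal, 98% with 1 point worse).

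**Step 4: arm sizes.** At 37/38 the planned C-D half-widths at 94.4% are 0.129 (equal) and 0.132 (1 point worse).

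**Step 5: sensitivity to the reading of the method.** With continuity correction the C-D table runs from 0.122 to 0.148. Score intervals by test inversion, with or without the Miettinen-Nurminen variance factor, give about 0.125 to 0.129 for C-D at 94.4%. Whole counts agree: 38/40 against 38/40 gives Wald 0.096 and planned 0.121.

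**The case against.** The best defence is that little hangs on these tables. No margin, power calculation or decision rule uses a half-width; the primary differences are only summarised with intervals; arm sizes followed observed enrolment; and the reported interval will be computed as specified whatever 8.2 says. That stands, and it makes this a correction to the planning figures, not a flaw in the analysis.

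The second defence is the hedge in the 11% sentence. Across both tables, with a deficit of 0 or 1 point, 13 of 20 cells still meet 11% under the planned method. But the sentence is tied to 94.4%, where only 2 of 4 cases meet it, and the misses are both C-D cases. The hedge does not cover one whole primary comparison.

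Third, the protocol does not name the Newcombe form. That is true, but no variant checked brings C-D at 94.4% back to 11%.

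Three stronger readings might be inferred and are not supported:

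- That the stated C-D values are 17-67% too small. Those percentages are the excess of the planned values over the stated ones; the shortfall is about 14-40%.
- That the 11% statement fails altogether. Every A-B cell stays below 11% (maximum 0.103).
- That 8.2 understates how much worse 12 weeks could be in non-cirrhotic subjects. The A-B lower distance is slightly shorter than the Wald half-width in all 15 cells (ratio 0.92 to 0.99; 0.074 against 0.078 at 94.4%). Only the upper side is longer.

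**Conclusion.** The point holds for the stated precision. Section 8.2 tabulates Wald half-widths for differences whose interval 8.1.2.1 fixes as Wilson's score method. For C-D at 40/40 the planned half-widths are 0.103-0.131 against the stated 0.061-0.112, and at 94.4% they are 0.124 and 0.126, so the 11% statement is wrong for that comparison.

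For A-B the effect is modest and the 11% statement survives. What a single half-width hides there is asymmetry: with 94.4% in both arms the interval runs from about −7.4 to +10.5 points.

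The figures assume the Newcombe interval without continuity correction, half-width meaning half of the full width, and the protocol's own rates and arm sizes. The documents do not support inferring that the planned analysis itself is invalid.

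**What to change.** In Protocol 8.2:

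1. Recompute both tables with the interval fixed in 8.1.2.1, and name the method and its variant beside them.
2. Give lower and upper distances separately, since the A-B interval is clearly asymmetric.
3. Use C-D arm sizes consistent with the cap of 75 cirrhotic subjects (about 37/38). The tabulated 40/40 needs 80.
4. Replace the single 11% sentence with one figure per comparison at 94.4%: about 9% for A-B and about 12-13% for C-D (0.124-0.126 at 40/40; 0.129-0.132 at 37/38).

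The cost is a less favourable stated precision for both comparisons, chiefly C-D. Patients, procedures and the analysis method do not change.
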